#### **4.2.2.3 Secondary outcome 3**

To describe health care resources use related to management of ES-SCLC patients treated with durvalumab in combination with platinum– etoposide as first-line treatment.

This analysis will be performed for the Intention-to-Treat population (ITT). To investigate the impact of treatment and disease on health care resource use, the following variables will be captured:

- Number of hospitalizations (Categorical and continuous)
- Length of hospitalizations: time from date of admission to discharge date (Continuous)
- Number of visits to oncology service (Categorical and continuous)
- Number of emergency visits (Categorical and continuous)
- Number of outpatients visits (Categorical and continuous)
- Number of imaging tests (Categorical and continuous)
- Number of biopsy-related procedures (Categorical and continuous)
- Listing of treatments administered, including: Treatment name, dose, duration and number of cycles (Categorical)
- Assessment of health economic resource: Costs associated with HCRU use will be quantified by multiplying the natural units of use of each resource by the cost of each resource retrieved from Spanish databases. It will be described the overall costs and health care resources use as well as costs and health care resources use adjusted by time in years.

### **4.3 Other variables and covariates**

#### **4.3.1 Screening failure**

A detailed listing of screening failure patients will be provided, containing the following information:

- Site
- Patient ID

- Screening failure reason: If not compliance with any inclusion/exclusion criteria, criteria will be provided. If other reason, specific reason will be provided.
- Re-screening (Yes; No). If affirmative:
  - Date of re-screening.

#### 4.3.2 Demographic data and clinical characteristic

The demographic, baseline description and clinical characteristics will be performed for the Intent-to-treat (ITT) population. The following variables will be described:

- Age (Categorical and continuous): Categorical data will be provided by defining two categories: <65 years and >65 years
- Gender (Categorical)
- Race (Categorical)
- Ethnicity (Categorical)
- Status of cigarette smoking (Categorical). If former or current smoker:
  - Number pack/year (Continuous)
- Vital signs at baseline:
  - Height (Continuous)
  - Weight (Continuous)
  - SBP (Continuous)
  - DBP (Continuous)
  - Pulse (Continuous)
  - Respiratory rate (Continuous)
  - Temperature (Continuous)
- Physical exam at baseline:
  - System (Categorical)
  - Finding (Categorical)
- Medical history (Yes; No): If affirmative:
  - Illness/Surgery/Intercurrent illness (Categorical)
- Serology:
  - Tuberculosis (Categorical)
  - HBsAg (Categorical)
  - HCV ab (Categorical): If positive:
    - HCV-RNA (Categorical)
  - VIH
- ECG (Done; Not done): If done:
  - Overall evaluation (Categorical): If abnormal:
    - Listing of the abnormalities detected, including if clinically significant.
- Charlson comorbidity index available (Yes; No): If affirmative:
  - Myocardial infarction (Yes; No) (Categorical)
  - Congestive heart failure (Yes; No) (Categorical)
  - Peripheral vascular disease (Yes; No) (Categorical)
  - Cerebrovascular disease (Yes; No) (Categorical)

- Dementia (Yes; No) (Categorical)
- Chronic obstructive pulmonary disease (Yes; No) (Categorical)
- Connective tissue disease (Yes; No) (Categorical)
- Peptic ulcer disease (Yes; No) (Categorical)
- Chronic liver disease mild (Yes; No) (Categorical)
- Diabetes mellitus (mild) (Yes; No) (Categorical)
- Hemiplegic (Yes; No) (Categorical)
- Chronic Kidney disease moderate-severe (Yes; No) (Categorical)
- Diabetes mellitus with lesion in target organ (moderate-severe) (Yes; No) (Categorical)
- Tumor or solid neoplasia (Yes; No) (Categorical)
- Leukemia (Yes; No) (Categorical)
- Lymphoma (Yes; No) (Categorical)
- Chronic liver disease moderate-severe (Yes; No) (Categorical)
- Tumor or solid neoplasia with metastasis (Yes; No) (Categorical)
- Acquired immunodeficiency syndrome (AISD) (Yes; No) (Categorical)
- Total score (Continuous)
- Presence of other comorbidities (Yes; No): If affirmative:
  - Other comorbidities (Categorical)

#### **4.3.3 Cancer history & Performance status**

The following cancer history data will be described for the for the Intent-to-treat (ITT) population.

- WHO/ECOG-PS (Categorical): It will be described at baseline, start of chemotherapy phase, start of post-chemotherapy phase and end of study.
- Subject autonomy (Categorical): It will be described at baseline, start of chemotherapy phase, start of post-chemotherapy phase and end of study.
- Time from initial diagnosis (Continuous): Defined as time, in months, from initial diagnosis date to informed consent date (enrolment in the study).
- Histology (Categorical)
- Initial stage (Categorical):
- Initial TNM stage (Categorical)
- Actual stage (Categorical)
- Actual TNM stage (Categorical)
- Primary tumor location (Categorical)
- Metastatic location (Yes; No) (Categorical). If affirmative:
  - Number of metastatic locations (Continuous)
  - Metastatic location (Categorical):
    - It will be provided the frequency of brain or CNS metastases (Categorical)
    - It will be provided the frequency of liver metastases (Categorical)
- Family history of cancer (Yes, No): If affirmative:

- Cancer type (Categorical)
- Relative degree per cancer type (Categorical)

#### 4.3.4 Treatment description

##### 4.3.4.1 Chemotherapy phase (Cycle 1 to 4-6)

This analysis will be performed for the Intention-to-Treat population (ITT). Treatment duration will be defined as time elapsed between treatment end date and treatment start date in chemotherapy phase. It will be described as continuous data for durvalumab, etoposide and platinum.

It will be described the number of cycles administered as continuous data. It will be considered as cycle administered when the patient receives a complete pattern of durvalumab + EP.

Additionally, the following data will be described:

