4.3.1.3 Rationale for durvalumab + EP dosing regimen

The dose and schedule of durvalumab proposed for this trial is consistent with that employed in the Phase III CASPIAN trial: a fixed dose of 1500 durvalumab Q3W while administered with chemotherapy followed by a fixed dose of 1500 mg durvalumab Q4W while administered as monotherapy maintenance until disease progression (Paz-Ares 2019). Likewise, the dose and schedule of etoposide and either carboplatin or cisplatin are consistent with those employed in the phase III CASPIAN trial as well as clinical practice guidelines (Paz-Ares 2019).

This trial will allow up to a maximum of 6 cycles of durvalumab + EP to be administered Q3W. While the CASPIAN trial allowed a maximum of 4 doses of durvalumab + EP, clinical practice guidelines have recommended between 4-6 doses of chemotherapy for treatment of ES SCLC (NCCN, ESMO). In the CASPIAN trial, 57% of patients in the control arm received 6 cycles of EP (Paz-Ares 2019), reflecting the importance of flexibility when determining the actual number of cycles of chemotherapy in clinical practice and the need to obtain safety data on the use of up to 6 cycles of durvalumab + EP. Therefore, this trial will allow up to 6 cycles of Durvalumab + EP.

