6.1 Treatments administered

6.1.1 Investigational products

AstraZeneca will supply durvalumab (MEDI4736). SoC agents platinum (carboplatin or cisplatin) and etoposide will be supplied locally, as it is the standard treatment for these patients according usual clinical practice.

Table 5 Study treatments

	Durvalumab	Etoposide	Cisplatin	Carboplatin
Study treatment name:	Durvalumab (MEDI4736)	Etoposide	Cisplatin	Carboplatin
Dosage formulation:	500-mg vial solution for infusion after dilution, 50 mg/mL	Sourced locally by site	Sourced locally by site	Sourced locally by site
Route of administration	IV	IV	IV	IV
Dosing instructions:	Durvalumab 1500 mg via IV infusion over 60 minutes on Day 1 of each cycle.	Etoposide sequentially administered per local standards (usually over 30 to 60 minutes IV infusion) on Days 1, 2, and 3 of each cycle.	Cisplatin as an IV infusion per local standards (usually over 60 to 120 minutes on Day 1) of each cycle.	Carboplatin as an IV infusion per local standards (usually over 30 to 60 minutes on Day 1) of each cycle.
Packaging and labelling	500-mg vial solution for infusion after dilution. ^b	Sourced locally by site	Sourced locally by site	Sourced locally by site
Provider	AstraZeneca	Sourced locally by site	Sourced locally by site	Sourced locally by site

^a Label text prepared for durvalumab (MEDI4736) will show the product name as “MEDI4736” or “durvalumab (MEDI4736)” depending upon the agreed product name used in the approved study master label document. All naming conventions are correct during this transitional period. Each vial will be labelled in accordance with Good Manufacturing Practice (GMP) Annex 13 and per country regulatory requirement.

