6.1.1.3 Order of Administration

Patients will receive durvalumab (1500 mg) via IV infusion over 60 minutes.

We recommend a 60-minute observation period after durvalumab is administered at least for cycle 1.

If no issues are seen after durvalumab is given during the first cycle, we recommend reducing the observation period after durvalumab administration to 30 minutes.

Durvalumab infusion will then be followed by administration following local standards of an IV infusion of carboplatin usually over 30 to 60 minutes or cisplatin usually over 60 to 120 minutes, followed by etoposide sequentially administered usually over 30 to 60 minutes infusion on Day 1 of each combination cycle; etoposide will also be administered as an IV infusion on days 2 and 3 of each cycle up until a maximum of 6 cycles has been reached.

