8.4.5 Management of IP-related toxicities

The following general guidance should be followed for management of toxicities.

- Treat each of the toxicities with maximum supportive care (including holding the agent suspected of causing the toxicity if required).

- If the symptoms promptly resolve with supportive care, consideration should be given to continuing the same dose of the assigned IP along with appropriate continuing supportive care. If medically appropriate, dose modifications are permitted
- All dose modifications should be documented with clear reasoning and documentation of the approach taken.
- In the event that durvalumab is temporarily discontinued or delayed as part of the toxicity management guidance, EP should still be administered as scheduled; every effort should be made to ensure patients receive at least 4 cycles of EP in the study, if conditions allow.
- In the event that EP is delayed, durvalumab should also be delayed and to be resumed as soon as feasible. Every effort should be made to ensure patients receive at least 4 cycles of EP, if conditions allow.

All toxicities will be graded according to NCI CTCAE, Version 5.0.

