#### **Durvalumab**

- Durvalumab total dose administered (mg) (Continuous)
- Number of durvalumab doses (Categorical and continuous):
  - It will be provided the number and percentage of patients receiving 12 or more durvalumab doses (Categorical)
- Duration of treatment with durvalumab in weeks (Continuous)
- Treatment interruption (Yes, No): If affirmative:
  - Number and percentage of patients with at least one treatment interruption
  - Reason for interruption (Categorical)
  - Total number of cycles interrupted and percentage regarding total cycles

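### SAP 4.3.4.1 counts only complete durvalumab + EP cycles, gives EP cycles no counting rule, and tabulates 12 or more durvalumab doses in a phase that allows at most 6

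*SAP*

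**What the plan says.** For the chemotherapy phase, SAP 4.3.4.1 states: "It will be described the number of cycles administered as continuous data". It then gives its only definition of a cycle in that phase: "It will be considered as cycle administered when the patient receives a complete pattern of durvalumab + EP". What makes a pattern complete is not defined.

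Below that, the section adds two component blocks.

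- The durvalumab block summarises the number of doses and the interruptions, and adds a threshold row: "It will be provided the number and percentage of patients receiving 12 or more durvalumab doses (Categorical").
- The EP block gives the patients reaching at least 4, 5 and 6 EP cycles, with interruptions, delays and reductions.
- In both blocks, interrupted cycles are also expressed as a percentage of total cycles. Neither an EP cycle nor total cycles is defined.

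SAP 4.3.4.2 has its own row for 12 or more cycles, but it covers durvalumab monotherapy only. SAP 5.2.1 allows subgroup comparisons of PFS, ORR, DoR and OS by number of chemotherapy cycles (5 or 6 versus 4 or fewer), again with no counting rule.

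On delivery of treatment, Protocol 8.4.5 says: "In the event that durvalumab is temporarily discontinued or delayed as part of the toxicity management guidance, EP should still be administered as scheduled". Protocol 4.3.1.3 sets the cap: "This trial will allow up to a maximum of 6 cycles of durvalumab + EP to be administered Q3W". Protocol Table 5 gives the durvalumab schedule: "Durvalumab 1500 mg via IV infusion over 60 minutes on Day 1 of each cycle".

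**The concern.** The SAP's cycle rule does not match how the protocol foresees treatment being given. A cycle in which EP was given while durvalumab was on hold is a real chemotherapy cycle, yet the summary of cycles administered treats it as not administered. The loss is not spread evenly, because it falls on patients whose durvalumab was held for toxicity. Protocol 4.3.1.3 justifies the trial partly by the need for safety data on up to 6 cycles of the combination, so readers will use this summary to see how much treatment patients received.

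Because it is the only chemotherapy-phase definition in the SAP, a programmer could also carry it into the tables that have no rule of their own: the EP cycle rows, the interruption percentages and the cycle-number subgroups. SAP section 7 schedules section 4.3.4 for the October 2021 interim output, together with the primary safety summaries, so the choice affects the first exposure tables.

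The 12-dose row is a separate fault. As placed, it describes a phase in which that number of doses cannot occur.

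**Working it through.** The plan states no figure that depends on this point, so there is nothing to reproduce first. The check compares the rules and does simple arithmetic.

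**1. Effect of the cycle rule.** Inputs: the complete-pattern rule (SAP 4.3.4.1) and continued EP during a durvalumab hold (Protocol 8.4.5).

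Counted cycles = EP cycles given − EP-only cycles.

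- Five EP cycles, durvalumab held in one: 5 − 1 = 4 counted.
- Six EP cycles, durvalumab held in cycles 2 to 4: 6 − 3 = 3 counted.

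Counted on EP alone, these patients have 5 and 6 cycles.

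**2. Possible effect on interruption percentages.** If total cycles meant complete cycles, the second patient's durvalumab interruption figure would be 3/3 = 100% instead of 3/6 = 50%. With four of six doses held it would be 4/2 = 200%. The SAP does not say which denominator applies.

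**3. How often this could happen (illustration only).** The documents give no hold rate. Assume an independent hold probability h per cycle after cycle 1, with h = 2%, 5% or 10%.

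P(at least one uncounted cycle in n) = 1 − (1 − h)^(n−1).

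| EP cycles | h = 2% | h = 5% | h = 10% |
|---|---|---|---|
| 4 | 5.9% | 14.3% | 27.1% |
| 5 | 7.8% | 18.5% | 34.4% |
| 6 | 9.6% | 22.6% | 41.0% |

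**4. Possible effect on the SAP 5.2.1 subgroup, only if the complete-pattern rule were used there.** A patient with 5 EP cycles moves to the group with 4 or fewer after one hold: 7.8%, 18.5% or 34.4%, as in the table. A patient with 6 EP cycles needs at least two holds in five later cycles: 1 − (1 − h)^5 − 5h(1 − h)^4 = 0.4%, 2.3% or 8.1%.

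**5. The 12-dose row.** Inputs: at most 6 combination cycles (Protocol 4.3.1.3; Protocol 6.1.1.3 also limits EP to "up until a maximum of 6 cycles has been reached") and one durvalumab dose per cycle (Protocol Table 5).

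Maximum doses in the phase = 6 × 1 = 6, which is below 12. The row is 0 of about 85 patients whatever the data.

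Over both phases, 12 doses can be reached. With c combination cycles, monotherapy starts 3 weeks after the last combination infusion and then runs every 4 weeks (SAP 4.1.2). The 12th dose therefore falls at week 3c + 4(12 − c − 1) without delays.

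- c = 4: 8 monotherapy doses needed, week 12 + 28 = 40.
- c = 5: 7 needed, week 15 + 24 = 39.
- c = 6: 6 needed, week 18 + 20 = 38.

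The monotherapy row in SAP 4.3.4.2 does not capture these patients. It asks for 12 monotherapy cycles, whereas they have 6 to 8.

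**The case against.** The strongest reply is that the SAP already plans most of what is needed. Durvalumab doses and EP cycles have their own blocks, and a count of complete combination cycles is a sensible measure of the exposure that Protocol 4.3.1.3 wants to study. That stands. The fault is that this count is presented as cycles administered, and that the EP rows have no rule. It would be wrong to infer that EP-only cycles vanish from every table.

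Other stronger readings are tempting but not supported:

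- **The cycle-number subgroup is misclassified.** SAP 5.2.1 refers to chemotherapy cycles, which most naturally means EP cycles, and the analyses are optional. The error arises only if the complete-pattern rule is carried over.
- **The primary safety results are distorted.** They are numbers and proportions of patients with events. They are not adjusted for cycles, and the safety subgroups in SAP 5.1 do not include cycle number.
- **The resource-use endpoint is miscounted.** Number of cycles in Protocol Table 3 is delivered through a separate treatment listing in SAP 4.2.2.3 and 5.2.3, which nothing ties to this rule.
- **One omitted etoposide day removes the cycle.** The term complete is undefined, so this is possible but not stated.
- **EP-only cycles will be common.** Protocol 8.4.5 delays durvalumab whenever EP is delayed, and Protocol 7.1 stops both when a discontinuation criterion is met. EP-only cycles therefore come mainly from temporary durvalumab holds, at an unknown rate.
- **The 12-dose row was planned as an empty table.** It may be a whole-treatment row in the wrong place. The durvalumab duration line in the same block carries no phase label, and the EP block includes cranial irradiation given after the combination cycles. Even so, the row sits under the chemotherapy-phase heading and the SAP has no whole-treatment exposure section, so its scope must be stated.

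**Conclusion.** The point holds as two wording faults in the exposure section. First, the summary of cycles administered drops one cycle for every EP-only cycle. This follows directly from SAP 4.3.4.1 read with Protocol 8.4.5 and needs no assumption beyond some durvalumab holds occurring. Its overall size cannot be given, because the documents state no hold rate; the percentages above show only a range under assumed rates. Any effect on the EP cycle rows, the interruption percentages or the SAP 5.2.1 subgroups depends on which count is programmed, so those are ambiguous rather than wrong. Second, the 12-dose row is 0% by construction where it stands, and as laid out no whole-treatment figure is specified.

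The primary adverse event incidences do not change. The point is worth correcting because the stated rules give an understated count and an empty row, and correction is cheap. It concerns counting only; no view is taken on when durvalumab or EP should be held or given.

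**What to change.** Revise SAP 4.3.4.1 and the related tables as follows.

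1. Label the existing count as complete durvalumab + EP cycles, and state what makes a cycle complete.
2. Define an EP cycle as one in which any platinum or etoposide was given, and a durvalumab dose as any administration of durvalumab.
3. Use the EP count for the rows on 4, 5 and 6 or more EP cycles, and for the cycle-number subgroups in SAP 5.2.1.
4. Use cycles started as the denominator for the interruption percentages.
5. Move the row for 12 or more durvalumab doses to an exposure summary over both phases combined.

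The cost is SAP wording and table shells. No new data should be needed, since Protocol 6.3 already has schedule changes, delays, interruptions, reductions and discontinuations recorded in the eCRF.

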#### **Durvalumab**

- Durvalumab total dose administered (mg) (Continuous)
- Number of durvalumab doses (Categorical and continuous):
  - It will be provided the number and percentage of patients receiving 12 or more durvalumab doses (Categorical)
- Duration of treatment with durvalumab in weeks (Continuous)
- Treatment interruption (Yes, No): If affirmative:
  - Number and percentage of patients with at least one treatment interruption
  - Reason for interruption (Categorical)
  - Total number of cycles interrupted and percentage regarding total cycles

#### **EP**

- Platinum administered (Cisplatin; Carboplatin): The following data will be described for each category.
- Total dose administered (mg) (Continuous)
- Total dose programmed (mg/m^2 for Cisplatin / AUC for Carboplatin) (Continuous)
- Number and percentage of patients receiving 4 or more cycles of EP (Categorical)
- Number and percentage of patients receiving 5 or more cycles of EP (Categorical)
- Number and percentage of patients receiving 6 or more cycles of EP (Categorical)
- Duration of EP treatment in weeks (Continuous)
- Treatment interruption (Yes, No): If affirmative:
  - Number and percentage of patients with at least one treatment interruption
  - Reason for interruption (Categorical)
  - Total number of cycles interrupted and percentage regarding total cycles
- Dose delay (Yes, No): If affirmative:
  - Number and percentage of patients with at least one dose delay
  - Reason for delay (Categorical)
- Dose reduction (Yes, No): If affirmative:

- Number and percentage of patients with at least one dose reduction
- Reason for reduction (Categorical)
- Number and percentage of patients who received prophylactic cranial irradiation (PCI) in patients showing complete or partial responses after the durvalumab + EP combination cycles will be described. To calculate the number of patients receiving PCI, the information collected on concomitant study medication will be considered.

#### **4.3.4.2 Post-Chemotherapy phase (Cycle 5-7 to X): Durvalumab monotherapy**

This analysis will be performed for the Intention-to-Treat population (ITT). Treatment duration will be defined as time elapsed between treatment end date and treatment start date in post-chemotherapy phase. It will be described as continuous data.

In will be considered as cycle administered when the patient receives at least one dose of durvalumab in post-chemotherapy phase. It will be described the number of cycles administered as continuous data. It will be described the number and percentage of patients with 12 cycles or more (Categorical).

Additionally, the following data will be described:

- Durvalumab total dose administered (mg) (Continuous)
- Duration of post-chemotherapy treatment with durvalumab in weeks (Continuous)
- Treatment interruption (Yes, No): If affirmative:
  - Number and percentage of patients with at least one treatment interruption
  - Reason for interruption (Categorical)
  - Total number of cycles interrupted and percentage regarding total cycles
- Dose delay (Yes, No): If affirmative:
  - Number and percentage of patients with at least one dose delay
  - Reason for delay (Categorical)

## **5. ANALYSIS METHODS**

Descriptive statistics will be used for all variables, as appropriate. Continuous variables will be summarized by the number of observations, mean, standard deviation, median, quartiles (Q1 and Q3), minimum, and maximum. Categorical variables will be summarized by frequency counts and percentages for each category. The number of missing data will be provided for every analysed variable.

Missing values will not be considered for calculating percentages or any other descriptive, meaning that only valid values will be presented. No use of any method for the handling of missing data is foreseen.

For patients excluded from the statistical analyses, descriptive of the reasons for non-evaluability will be provided.

The software package SAS version 9.4 will be used for data analysis.

